7.3.3 Interaction with other medications

Potential drug-drug interactions between bavituximab and docetaxel were investigated in 17 patients, which showed no significant differences in PK parameters when bavituximab was administered with or without docetaxel.⁴²

7.3.4 Adverse Reactions

No adverse reactions are known to be specifically attributable to bavituximab. All serious adverse events will be reported to the Sponsor.

7.4 Adverse Event Monitoring

Adverse event data collection and reporting, which are required as part of every clinical trial, are done to ensure the safety of subjects enrolled in the studies as well as those who will enroll in future studies. Adverse events are assessed in a routine manner at scheduled times during a trial. Additionally, certain adverse events must be reported in an expedited manner to allow for optimal monitoring of subject safety and care.

All subjects experiencing an adverse event, regardless of its relationship to study therapy, will be monitored until:

- the adverse event resolves or the symptoms or signs that constitute the adverse event return to baseline or is stable in the opinion of the investigator;
- there is a satisfactory explanation other than the study therapy for the changes observed; or
- death.

7.4.1 Definitions

An adverse event is defined as any untoward or unfavorable medical occurrence in a human research study participant, including any abnormal sign (for example, abnormal physical exam, imaging finding or clinically significant laboratory finding), symptom, clinical event, or disease, temporally associated with the subject's participation in the research, whether or not it is considered related to the subject's participation in the research.

Adverse events encompass clinical, physical, and psychological harms. Adverse events occur most commonly in the context of biomedical research, although on occasion, they can occur in the context of social and behavioral research. Adverse events may be expected or unexpected.

Severity

Adverse events will be graded by a numerical score according to the defined NCI Common Terminology Criteria for Adverse Events (NCI CTCAE) Version 5.0. Adverse events not specifically defined in the NCI CTCAE will be scored on the Adverse Event log according to the general guidelines provided by the NCI CTCAE and as outlined below.

- Grade 1: Mild
- Grade 2: Moderate
- Grade 3: Severe or medically significant but not immediately life threatening
- Grade 4: Life threatening consequences
- Grade 5: Death related to the adverse event

Serious Adverse Events

OHRP and UTSW HRPP define serious adverse events as those events, occurring at any dose, which meets any of the following criteria:

- results in death;
- is life-threatening (places the subject at immediate risk of death from the event as it occurred);
- results in inpatient hospitalization^{1,2} or prolongation of existing hospitalization;
- results in a persistent or significant disability/incapacity;

- results in a congenital anomaly/birth defect; or
- based upon appropriate medical judgment, may jeopardize the subject's health, and may require medical or surgical intervention to prevent one of the other outcomes listed in this definition.

Note: A "Serious adverse event" is, by definition, an event that meets **any** of the above criteria. Serious adverse events may or may not be related to the research project. A serious adverse event determination does not require the event to be related to the research. That is, both events completely unrelated to the condition under study and events that are expected in the context of the condition under study may be serious adverse events, independent of relatedness to the study itself. As examples, a car accident requiring ≥ 24 -hour inpatient admission to the hospital would be a serious adverse event for any research participant; likewise, in a study investigating end-stage cancer care, any hospitalization or death which occurs during the protocol-specified period of monitoring for adverse and serious adverse events would be a serious adverse event, even if the event observed is a primary clinical endpoint of the study.

¹Pre-planned hospitalizations or elective surgeries are not considered SAEs. Note: If events occur during a pre-planned hospitalization or surgery, that prolong the existing hospitalization, those events should be evaluated and/or reported as SAEs.

² NCI defines hospitalization for expedited AE reporting purposes as an inpatient hospital stay equal to or greater than 24 hours. Hospitalization is used as an indicator of the seriousness of the adverse event and should only be used for situations where the AE truly fits this definition and NOT for hospitalizations associated with less serious events. For example: a hospital visit where a patient is admitted for observation or minor treatment (e.g. hydration) and released in less than 24 hours. Furthermore, hospitalization for pharmacokinetic sampling is not an AE and therefore is not to be reported either as a routine AE or in an expedited report.

7.4.2 Unanticipated Problems Involving Risks to Subjects or Others (UPIRSOs):

The phrase "unanticipated problems involving risks to subjects or others" is found, but not defined in the HHS regulations at 45 CFR 46, and the FDA regulations at 21 CFR 56.108(b)(1) and 21 CFR 312.66. For device studies, part 812 uses the term unanticipated adverse device effect, which is defined in 21 CFR 812.3(s). Guidance from the regulatory agencies considers unanticipated problems to include any incident, experience, or outcome that meets ALL three (3) of the following criteria:

- Unexpected in terms of nature, severity or frequency given (a) the research procedures that are described in the protocol-related documents, such as the IRB-approved research protocol and informed consent document; and (b) the characteristics of the subject population being studied;
AND
- Related or possibly related to participation in the research (possibly related means there is a reasonable possibility that the incident, experience, or outcome may have been caused by the procedures involved in the research);
AND
- Suggests that the research places subjects or others at greater risk of harm (including physical, psychological, economic, or social harm) than was previously known or recognized. Note: According to OHRP, if the adverse event is serious, it would always suggest a greater risk of harm.

Follow-up

All adverse events will be followed up according to good medical practices.

7.5 Expedited Reporting to the SCCC DSMC

Step 1: Identify the type of adverse event using the NCI Common Terminology Criteria for Adverse Events (CTCAE v5).

Step 2: Grade the adverse event using the NCI CTCAE v5.

Step 3: Determine whether the adverse event is related to the protocol therapy.

Attribution categories are as follows:

- Definite – The AE *is clearly related* to the study treatment.
- Probable – The AE *is likely related* to the study treatment.
- Possible – The AE *may be related* to the study treatment.
- Unlikely – The AE *may NOT be related* to the study treatment.
- Unrelated – The AE *is clearly NOT related* to the study treatment.

Note: This includes all events that occur within 30 days of the last dose of protocol treatment. Any event that occurs more than 30 days after the last dose of treatment and is attributed (possibly, probably, or definitely) to the agent(s) must also be reported as indicated in the sections below.

Step 4: Determine the prior experience of the adverse event. Expected events are those that have been previously identified as resulting from administration of the treatment. An adverse event is considered unexpected, for expedited reporting purposes only, when either the type of event or the severity of the event is not listed in:

- the current known adverse events listed in the Agent Information Section of this protocol (if applicable);
- the drug package insert (if applicable);
- the current Investigator's Brochure (if applicable)
- the Study Agent(s)/Therapy(ies) Background and Associated Known Toxicities section of this protocol

7.5.1 Reporting SAEs and UPIRSOs to the Simmons Comprehensive Cancer Center (SCCC) Data Safety Monitoring Committee (DSMC)

SAEs and UPIRSOs at all sites, which occur in research subjects on protocols for which the SCCC is the DSMC of record require reporting to the DSMC regardless of whether IRB reporting is required. All SAEs occurring during the protocol-specified monitoring period and all UPIRSOs should be submitted to the SCCC DSMC within 5 business days of the study team members awareness of the event(s). In addition, for participating centers other than UTSW, local IRB guidance should be followed for local reporting of serious adverse events or unanticipated problems.

1. Unexpected in nature, frequency, or severity (i.e., generally not expected in a subject's underlying condition or not expected as a risk of the study; therefore, not included in the investigator's brochure, protocol, or informed consent document), AND
2. Probably or definitely related to participation in the research, AND
3. Suggests that the research places subjects or others at a greater risk of harm (including physical, psychological, economic, or social harm) than was previously known or recognized. Note: According to OHRP, if the adverse event is serious, it would always suggest a greater risk of harm.

For purposes of this policy, UPIRSOs include unanticipated adverse device effects (UADEs) and death or serious injury related to a humanitarian use device (HUD).

UPIRSOs must be promptly reported to the UTSW HRPP within 5 working days of study team awareness.

For research relying on a non-UT Southwestern IRB (external, central, or single IRB):

Investigators relying on an external IRB who are conducting research on behalf of UT Southwestern or its affiliates are responsible for submitting **LOCAL** UPIRSOs to the UT Southwestern IRB within 5 working days of study team awareness. Investigators must report to their relying IRB according to the relying IRB's policy. In addition, the external IRB's responses or determinations on these local events must be submitted to the UT Southwestern IRB within 10 working days of receipt.

Events NOT meeting UPIRSO criteria:

Events that do NOT meet UPIRSO criteria should be tracked, evaluated, summarized, and submitted to the UTSW HRPP/IRB at continuing review.

For more information on UTSW HRPP/IRB reportable event policy, see <https://www.utsouthwestern.edu/research/hrpp/quality-assurance/>

7.6 Stopping Rules

This study utilizes a two-stage design which allows stopping for futility which minimizes the expected sample size when the true response is low. In the first stage, 14 evaluable patients will be accrued. The study will proceed to the second stage only if 2 or greater responses are observed. If less than 2 responses are observed among the first 14 evaluable patients, the study will be terminated.

8.0 DRUG/TREATMENT INFORMATION

8.1 Axitinib

- Other names for the drug(s): Inlyta
- Classification - type of agent: Targeted therapy
- Mode of action: Selective inhibitor of VEGFR-1, 2, and 3
- Storage and stability: Axitinib must be stored at controlled room temperature (between 15-30 C) or as specified in the product label.
- Protocol dose: 5 mg BID at approximately the same time in the morning and evening on a continuous dosing schedule. Axitinib tablets are to be taken approximately 12 hours apart and may be administered without regard to meals. Tablets must not be crushed, split, or dissolved, and patients should be instructed to swallow the study medication whole without manipulation or chewing of the medication prior to swallowing. A dosing card will be provided to the patients to provide guidance for the correct use of axitinib.
- Route of administration for this study: oral
- Availability: provided by Pfizer

- Side effects: The most common ($\geq 20\%$) adverse reactions observed following treatment with axitinib were diarrhea, hypertension, fatigue, decreased appetite, nausea, weight decreased, dysphonia, palmar-plantar erythrodysesthesia, hemorrhage, hypothyroidism, vomiting, proteinuria, cough, and constipation. See Section 7.1.4 and the axitinib Investigator's Brochure for additional information on expected treatment related AEs.

8.1.1 Return and Retention of Study Drug

Patients will be required to return to the investigational site all bottles of axitinib every 4 weeks (at the end of each cycle) during the planned visit at the site. The number of remaining axitinib tablets will be documented and recorded at each clinic visit. The patient diary may also be used to support this part of the axitinib accountability process.

The sponsor or designee will provide guidance on the destruction of unused investigational product. If destruction is authorized to take place at the study site, the investigator must ensure that the materials are destroyed in compliance with applicable environmental regulations, institutional policy, and any special instructions provided by Pfizer, and all destruction must be adequately documented.

- ### **8.1.2**
- A dosing card will be provided to the patients to provide guidance for the correct use of axitinib. Patients must be instructed that if they miss a dose or vomit any time after taking a dose, they must not "make it up" with an extra dose, but instead resume subsequent doses as prescribed. Any missed dose may be taken late, up to 3 hours before the next scheduled dose of that day, otherwise, it should be skipped and dosing resumed with subsequent doses as prescribed. Patient must be instructed to record all doses (missed or vomited doses or extra doses) in a dosing diary supplied by the site.

8.2 Avelumab

- Other names for the drug(s): Bavencio
- Classification - type of agent: Immunotherapy
- Mode of action: anti-PD-L1 antibody
- Storage and stability: Store at 2°C to 8°C and protected from light until use. Avelumab drug product must not be frozen. Rough shaking of the solution must be avoided.
- Protocol dose: 10 mg/kg every 2 weeks (maximum dose of 2000)
- Route of administration for this study: intravenous
- Avelumab will be dosed at the investigational site. Avelumab will be administered as a 1-hour (no longer than 2 hours) IV infusion on Day 1 and Day 15 of each 28-day cycle. Avelumab may be administered up to 3 days before or after the scheduled Day 1 of each dose due to administrative reasons. Avelumab should be administered at least 30 minutes after the bavituximab infusion (on days when both are administered). In order to mitigate infusion-related reactions, a required premedication regimen of 25 to 50 mg IV or oral equivalent diphenhydramine and 650 mg IV or oral equivalent acetaminophen will be administered immediately prior to administration of avelumab.

- The contents of the avelumab vials are sterile and nonpyrogenic, and do not contain bacteriostatic preservatives. Any spills that occur should be cleaned up using the facility's standard cleanup procedures for biologic products. Avelumab drug product must be diluted with preferably 250 mL 0.9% saline solution (sodium chloride injection) supplied in an infusion bag; alternatively, a 0.45% saline solution can be used if needed. If not used immediately, the diluted drug product can be stored up to 8 hours at room temperature or up to 24 hours at 2°C to 8°C. The storage conditions may be limited to up to 4 hours at room temperature depending on the approved avelumab label in the country. No other drugs should be added to the solution for infusion containing avelumab.

Detailed information on infusion bags and medical devices to be used for the preparation of the dilutions and subsequent administration will be provided in the Dosage and Administration Instruction contained in the Investigational Product Manual (IP Manual).

- Availability: provided by Pfizer
- Side effects: The most frequent AEs attributable to avelumab include infusion reactions and irAEs. See Section 7.2.4 and the avelumab Investigator's Brochure for additional information on expected treatment related AEs.

8.2.1 Return and Retention of Study Drug

The sponsor or designee will provide guidance on the destruction of unused investigational product. If destruction is authorized to take place at the study site, the investigator must ensure that the materials are destroyed in compliance with applicable environmental regulations, institutional policy, and any special instructions provided by Pfizer, and all destruction must be adequately documented.

8.3 Bavituximab

- Other names for the drug(s): none
- Classification - type of agent: Immunotherapy
- Mode of action: anti-phosphatidylserine antibody
- Storage and stability: Store at 2°C to 8°C. Once diluted, it should be stored at room temperature and used within 8 hours.
- Protocol dose: 3 mg/kg every week
- Route of administration for this study: intravenous
- Bavituximab will be dosed at the investigational site. Infusion preparation and administration are to be performed as follows:
 1. Draw up the volume of a vial using a sterile syringe attached to an appropriate needle (a vented spike or other appropriate transfer device may be used). Fill treatment into a sterile glass bottle or plastic IV bag.
 2. Using aseptic techniques, repeat procedure until the calculated volume has been put into the container. Bring the final volume to 100 mL using 0.9% Sodium Chloride Injection, USP.

3. Administer through a low protein binding 0.2-micrometer in-line filter (placed as proximal to the patient as practical).
4. Affix the infusion line and prime it with infusate before starting the infusion. Infuse the solution intravenously over 90 (\pm 10) minutes. No reduction in infusion time will be permitted. Flush the line with normal saline after infusion.

- Availability: provided by OncXerna
- Side effects: The most frequent AEs attributable to bavituximab include decreased appetite, fatigue, constipation, nausea, and diarrhea. See Section 7.3.4 for additional information on expected treatment related AEs.

8.3.1 Return and Retention of Study Drug

The sponsor or designee will provide guidance on the destruction of unused investigational product. If destruction is authorized to take place at the study site, the investigator must ensure that the materials are destroyed in compliance with applicable environmental regulations, institutional policy, and any special instructions provided by OncXerna, and all destruction must be adequately documented.

9.0 CORRELATIVES/SPECIAL STUDIES

The goal of the planned laboratory correlative studies is to assess genetic mechanisms of immunotherapy resistance. Analyses will be performed on tissue specimens collected as a component of routine clinical practice, and thus no additional specimen collection solely for research purposes is required.

Archival or baseline tumor tissue will be genomically characterized by MI Profile (Caris Life Sciences). This will allow us to assess whether mutations, copy number alterations, and RNA signatures may be associated with different clinical outcomes.

10.0 STATISTICAL CONSIDERATIONS

10.1 Study Design/Study Endpoints

The study is an open-label, non-randomized single-arm, multi-center phase II therapeutic clinical trial with a safety lead-in. The study population will be patients with advanced HCC.

Combination treatment with axitinib, avelumab, and bavituximab will be tested in a safety lead-in of the first 6 patients evaluable for dose-limiting toxicities in this study (see definitions for evaluable patients and dose-limiting toxicities in Section 4.2) to ensure the safety and tolerability of this triplet regimen.

A two-stage design is used to limit the maximum sample size required to determine efficacy. Objective response requires confirmation imaging greater than or equal to 4 weeks after initial best response. Patients who attain a complete response, partial response, or stable disease but do not have two imaging assessments to confirm response will be replaced. Patients who have progressive disease at any imaging assessment do not require subsequent confirmation.

10.2 Sample Size and Accrual

We will use a minimax two-stage design method to compare the objective response rate of 34% (alternative hypothesis) for the treatment cohort versus 14% (null hypothesis) for the historical control. The basis of the null response rate is based on the previously reported objective response rate of 14% for axitinib plus avelumab in advanced HCC. This design

requires a sample size of 29 evaluable patients to yield a type I error rate of 0.10 and power of 0.9 when the true response rate is 34%. In the first stage 14 evaluable patients will be accrued. If there are 2 or more responses, then 15 additional evaluable patients will be accrued. Thus, the total enrollment for this study will be up to 29 evaluable patients. The null hypothesis will be rejected if 7 or more responses are observed in 29 patients. Objective response rate is defined as number of responders (either complete or partial response as the best objective response) of eligible patients. Patients who attain a complete response, partial response, or stable disease but do not have two imaging assessments to confirm response will be replaced.

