Diagnosis and Main Inclusion Criteria	
 1. Patients must have a histologically confirmed diagnosis of hepatocellular carcinoma; 2. No history of prior systemic therapy for HCC; 3. Patients with advanced HCC not eligible for curative and/or locoregional therapies; 4. Age ≥ 18 years; 5. Child-Pugh Score A
Study Product(s), Dose, Route, Regimen	Axitinib 5 mg PO BID Avelumab 10 mg/kg IV every 2 weeks (maximal dose of 2000 mg; 2 doses in a 4-week cycle) Baviximab 3 mg/kg IV every 1 week (4 doses in a 4-week cycle)
Duration of administration	Study treatment will continue until disease progression, unacceptable toxicity, death, or discontinuation from the study treatment for any other reason.

Statistical Methodology	Safety and tolerability assessment will be performed for the first 6 evaluable patients in the safety lead-in. The primary endpoint of the trial will be objective response rate (ORR). A minimax two-stage method will be used to analyze ORR after the first 14 patients are accrued. 15 additional patients will be enrolled if 2 or more of the first 14 patients have either a complete or partial response.
-------------------------	---

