6.1.1 Definitions

Evaluable for toxicity. All subjects will be evaluable for toxicity from the time of their first treatment with study therapy.

Evaluable for objective response. Only those subjects who have measurable disease present at baseline, have received at least one cycle of therapy, and have had their disease re-evaluated will be considered evaluable for response. These subjects will have their response classified according to the definitions stated below. (Note: Subjects who exhibit objective disease progression prior to the end of cycle 1 will also be considered evaluable.)

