6.1.4.3 Evaluation of Best Objective Response

The best objective response is the best response recorded from the start of the treatment until disease progression/recurrence (taking as reference for progressive disease the smallest measurements recorded since the treatment started). The subject’s best response assignment will depend on the achievement of both measurement and confirmation criteria.

Time point response: patients with target (+/- non-target) disease.			
Target lesions	Non-target lesions	New lesions	Objective response
CR	CR	No	CR
CR	Non-CR/non-PD	No	PR
CR	Not evaluated	No	PR
PR	Non-PD or not all evaluated	No	PR
SD	Non-PD or not all evaluated	No	SD
Not all evaluated	Non-PD	No	NE
PD	Any	Yes or No	PD
Any	PD	Yes or No	PD
Any	Any	Yes	PD

CR = complete response, NE = not evaluable, PD = progressive disease, PR = partial response, SD = stable disease.

Time point response: patients with non-target disease only.		
Non-target lesions	New lesions	Objective response
CR	No	CR
Non-CR/non-PD	No	Non-CR/non-PD
Not all evaluated	No	NE
Unequivocal PD	Yes or No	PD
Any	Yes	PD

CR = complete response, NE = not evaluable, PD = progressive disease

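### The ORR and the 2/14 and 7/29 rules name different denominators, and treated patients who count as non-responders are replaced depending on outcome

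*Combined protocol and SAP*

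**What the plan says.** Section 10.2 sets both decision rules on evaluable patients: 14 in stage 1, 29 in total, and rejection of the null at 7 or more responses. Section 7.6 agrees: "If less than 2 responses are observed among the first 14 evaluable patients, the study will be terminated". Section 10.2 then defines the endpoint over another set: "Objective response rate is defined as number of responders (either complete or partial response as the best objective response) of eligible patients". Section 10.3 plans a Clopper-Pearson interval for the ORR and names no denominator.

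Under Section 6.1.1, patients with measurable disease who "have received at least one cycle of therapy, and have had their disease re-evaluated will be considered evaluable for response". Objective progression before the end of cycle 1 also makes a patient evaluable. No second scan is asked for. Sections 10.1 and 10.2 nevertheless add: "Patients who attain a complete response, partial response, or stable disease but do not have two imaging assessments to confirm response will be replaced".

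Two further statements decide how the replaced patients score. Section 10.1 says "Objective response requires confirmation imaging greater than or equal to 4 weeks after initial best response", and Section 6.1.4.3 says the "best response assignment will depend on the achievement of both measurement and confirmation criteria". For progression, Section 10.1 says "Patients who have progressive disease at any imaging assessment do not require subsequent confirmation".

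**The concern.** A patient with one scan showing stable disease (SD), or an unconfirmed complete or partial response (CR/PR), is evaluable under 6.1.1 and replaced under 10.1 and 10.2. By the plan's own confirmation rule that patient is not a responder. For SD, a second scan is not needed to know this, since SD is never an objective response. The patient nevertheless leaves the count and a new patient with a fresh chance of response comes in. A patient with progression, equally a non-responder, is kept. Replacement therefore depends on outcome.

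This affects the primary endpoint and the only futility rule, in an open-label trial with investigator-assessed response. If the denominator is not settled beforehand, it can be chosen after the results are known.

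**Working it through.** **1. The plan's own figures.** Inputs from Section 10.2: null 14%, alternative 34%, continue at 2 or more of 14, reject at 7 or more of 29. The exact probability of rejection is

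R(p) = Σ over x = 2 to 14 of P(X₁ = x | 14, p) × P(X₂ ≥ 7 − x | 15, p).

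R(0.14) = 0.0973 and R(0.34) = 0.9002. The stated 0.10 and 0.9 reproduce, with p as the response rate in the set that is counted to 14 and 29.

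**2. Same data, different stage 1 decision.** Suppose the first 14 treated patients include 1 confirmed response and 2 patients with a single SD scan, and all 14 are evaluable under 6.1.1. Without replacement the result is 1/14 and the trial stops. With replacement, two more patients are added and the trial continues if either responds:
- at a 14% response rate, 1 − 0.86² = 26%
- at 34%, 1 − 0.66² = 56%

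**3. Same data, different ORR.** With 3 patients replaced, seven responses are
- 7/29 = 24.1% (Clopper-Pearson 95% CI 10.3% to 43.5%), or
- 7/32 = 21.9% (9.3% to 40.0%).

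The 7-response boundary is set only for 29.

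**4. Effect on the chance of meeting 7/29.** Let d be the share of treated patients replaced. The documents do not give it, so 5%, 10% and 15% are assumed (about 1.5, 3.2 and 5.1 patients replaced to reach 29, from 29/(1 − d) − 29). Let f be the response rate credited to the replaced patients. If the rate over all treated patients is 14%, the rate in the counted set is (0.14 − d·f)/(1 − d).

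| f | d = 5% | d = 10% | d = 15% |
|---|---|---|---|
| 0 (confirmed responses only) | 0.120 | 0.148 | 0.183 |
| 7% | 0.108 | 0.121 | 0.137 |
| 14% | 0.097 | 0.097 | 0.097 |
| 25% | 0.081 | 0.066 | 0.051 |

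For example, at f = 0 and d = 10% the counted rate is 0.14/0.90 = 0.1556, and R(0.1556) = 0.148.

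The rows answer two questions. The first takes the plan's confirmation rule literally: replaced patients have no confirmed response. The other three ask what they would have shown had a second scan been done.

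**5. The benchmark.** Section 1.2.3 gives 13.6% (95% CI 2.9% to 34.9%) in 22 treated patients. That matches 3/22, whose exact interval is 2.9% to 34.9%. The documents do not say whether the three responses were confirmed.

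**The case against.** **One set was plainly intended.** Sections 7.6 and 10.2 repeatedly say evaluable, and *eligible* may be a slip. A reader might infer a third set from the Study Summary, which says "15 additional patients will be enrolled if 2 or more of the first 14 patients have either a complete or partial response". The documents do not support that: the Number of Subjects row of the same summary gives 14 to 29 evaluable patients, so the sentence is shorthand. This part of the objection stands. It does not remove the conflict between 6.1.1 and the replacement sentence, or the replacement of non-responders.

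**No type I error problem is shown.** A reader might infer from the first row of the table that the true error rate exceeds 0.10. The documents do not support that either. The stated alpha is correct for the evaluable rate. The replaced group excludes progression and includes unconfirmed responses, so its would-be response rate could exceed 14%, and replacement would then be conservative. The benchmark's confirmation status is also unknown. This stands in full.

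**The replaced share may be small.** Section 5.2.3 schedules tumor measurements at the end of treatment, so many patients who stop after one scan could have a second. This is fair, but the plan does not say whether that scan counts as the second assessment.

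**Counting all treated patients changes the estimand.** It does, and power may fall if 34% was meant for evaluable patients only. That cost is set out with the fix.

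**Conclusion.** The point holds as an inconsistent denominator combined with an outcome-dependent replacement rule, and it should be fixed. Neither defect rests on an assumed figure: both follow from the text of 6.1.1, 10.1 and 10.2, and the example in step 2 shows opposite stage 1 outcomes from the same 14 patients.

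The size does rest on assumptions. If replaced patients are scored as the confirmation rule requires, the chance of success at a 14% all-treated rate is 0.120 to 0.183 for 5% to 15% replaced. On would-be rates from 7% to 25%, it runs from 0.137 down to 0.051. The direction against the benchmark is therefore open. The two-stage calculation itself is sound.

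**What to change.** In the Study Summary and Sections 6.1.1, 7.6, 10.1 and 10.2, use one denominator for the ORR and both rules: all eligible patients who received at least one dose of study drug. Count patients with no post-baseline scan, a single SD scan or an unconfirmed CR/PR as non-responders. Delete the replacement sentence from 10.1 and 10.2, and replace only patients who never start study drug. Keep 2/14, 7/29 and N = 29. Report the evaluable-only ORR as a sensitivity analysis, with the number of patients excluded and the reasons.

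Aligning the words alone while keeping the replacement would not be enough, because non-responders would still be exchanged for new patients.

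The cost is that the reported ORR may be lower. If 14% and 34% are read as all-treated rates, alpha stays 0.0973 and power 0.900. If 34% was meant for evaluable patients only, the all-treated rate is 0.34 × (1 − d). At 5%, 10% and 15% non-evaluable, power is then about 0.86, 0.82 and 0.76, and the chance of a stage 1 stop rises from 2.4% to 3.3%, 4.3% and 5.6%. In that case restate the power rather than enlarge the trial.
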